functioning. Importantly, the proposed study will provide neuroimaging-based evidence for functional changes in the brain that underlie IASIS treatment effects in individuals with mTBI, independent of potential placebo effects. Information about the brain regions that generate abnormal MEG slow waves in each individual patient may also ultimately be used as a guide in developing optimal and subject-specific IASIS treatment protocols. We will also investigate the relationships among treatment-related changes in aberrant rs-MEG slow-wave generation and changes in PCS and neuropsychological measures, which may clarify specific behavioral sequelae that are more or less responsive to IASIS. High correlations between MEG slow-wave sources and clinical symptoms and/or cognitive dysfunction in mTBI patients will also significantly enhance the clinical relevance of MEG, advance its value for tracking the effects of recovery, and elucidate the source of post-mTBI cognitive deficits, which are controversial. Altogether, this study will substantially enhance our knowledge about the effect of transcranial electrical stimulation in mTBI mechanisms underlying LIP-tES, and its relevance to behavioral outcomes that significantly impact the quality of life in Veterans with mTBI.

B.5 Significance and Innovation: IASIS Effects on PTSD Symptoms

Veterans with mTBI often also have PTSD symptoms [25]. Many cross-sectional studies have found higher (nearly double) rates of PTSD in active-duty service members and Veterans with mTBI [27,76,77]. These findings have been corroborated using prospective study designs in civilians [78] and in two large active duty service members cohorts, the Marine Resiliency Study (MRS) and the Army Study to Assess Risk and

Resilience in Servicemembers (Army STARRS) [79,80]. Army STARRS reported a dose-response relationship between “very mild” (dazed but no loss of consciousness or amnesia), “mild” (some loss of consciousness or amnesia), and “more-than-mild” TBI and observed mental health outcomes, including PTSD [80]. These studies suggest that the extent of injury to the brain moderates the likelihood of the PTSD development. This view is consistent with a model in which TBI impairs functioning of prefrontal cortex that inhibits fear responses and promotes fear extinction [26,79]. Thus, we hypothesize that by treating mTBI using IASIS in Veterans with comorbid mTBI and PTSD, co-existing PTSD symptoms will also be reduced.

C. PRELIMINARY STUDIES

C.1 Voxel-wise Fast-VESTAL MEG Source

We have developed a high-resolution voxel-wise MEG source imaging technique called Fast-VESTAL [65] (see B.2). In the present application, we propose to use Fast-VESTAL for localizing abnormal MEG slowwaves in Veterans with mTBI. The first step is to obtain voxel-wise MEG sources images in HC subjects, which will lead to the establishment of voxel-wise normative databases. Fig. 1 displays Fast-VESTAL MEG source images for the four frequency bands (data from 41 HC subjects) [65]. Source images were plotted using the t-test between source magnitudes in HC subjects against empty room recordings when no subjects were in the MEG scanner. Despite resting-state alpha band (8 - 12 Hz) activity in humans being first detected by EEG [81] ~90 years ago and by MEG [82] ~50 years ago, Fig. 1 displays one of the first whole-brain voxel-wise MEG/EEG source images for resting-state signal (see [65] for details). Fig. 1 illustrates the feasibility of the voxel-wise MEG source imaging using Fast-VESTAL, and provides the foundation for establishing voxel-wise MEG normative HC database.

Figure 1 - See attached document.

C.2 Assessing the Positive Detection Rates of MEG Slow-wave Source Images in mTBI

We propose to study a voxel-wise MEG slow-wave source imaging approach for detecting mTBI on a single-subject basis. Fig. 2 shows Zcmax values (a measure of abnormal MEG slow-wave, see D.3.2) obtained from voxel-wise MEG source magnitude source imaging, plotted separately for 1) 79 HC, 2) 36 blast mTBIs, and 3) 48 non-blast mTBIs [1]. There was minimal overlap of Zcmax values between each mTBI group and the HC group, with the patients in all mTBI groups showing markedly higher slow-wave Zcmax values than the HC subjects. These results provide the foundation for assessing abnormality of mTBI on a single-subject basis using MEG slowwave source imaging. With a 2.5 threshold (horizontal line in Fig. 2), the positive detection rates were 86.1% for the blast mTBI patients, and 83.3% for the non-blast mTBI patients. After combining blast and non-blast mTBI groups together, the positive detection rate was 84.5% [1]. No HC subjects showed a Zcmax value above the threshold (i.e., apparent specificity of 100%) which was chosen based on Youden index (see D.3.6). In contrast, the positive detection rates using conventional MRI were 5.6%, 8.3%, and 7.1% for the same blast, non-blast, and combined mTBI groups, respectively. Based on the sensitivity defined in D.3.6, MEG slowwave source imaging was significantly more sensitive than MRI in detecting mTBI in the both blast and non-blast mTBI groups (McNemar test, $p < 10^{-6}$) [1], which strongly supports Hypothesis 1. The limitations of this study were: 1) most of the HCs (i.e., 68 out of 79) were civilians without combat exposure, whereas all patients in the blast mTBI group had combat exposure, with 24 out of 36 blast mTBI patients active-duty service members and the remaining 12 Veterans; 2) cross-validation of the voxel-wise normative database was not performed. The present application will directly address these limitations in our normative database using HC Veterans with matching combat exposure. **Figure 2 - See attached document.**

C.3 Preliminary Data from Individual mTBI Cases using Single-subject-basis Analysis

Although the analysis using Zcmax provides crucial information for positive detection rate that may assist in diagnosis in a single-subject basis, it does not address the loci and characteristics of abnormal slow-wave generation in individual mTBI patients. The voxel-wise framework based on Fast-VESTAL MEG source images identifies the sources of abnormal MEG slow-wave generation in individual mTBI patients. Fig. 3 shows the results of a single-subject-basis analysis that reveals statistically significant abnormal MEG slowwave generation (see D.3.5) from 8 representative mTBI cases in MNI space. The distribution of abnormal MEG slow-wave sources was in heterogeneous locations, but unique to individual mTBI patients, due to the nature of injuries. Such individualized information can be used to design optimal treatment strategies that target abnormal brain areas on a single-subject-basis. **Figure 3 - See attached document.**

C.4 Preliminary Data for Test-retest Reliability

Test-retest-reliability of single-subject MEG slow-wave imaging is an important component of the present application. In a pilot study, we examined test-retest-reliability of MEG slow-wave source imaging for three chronic mTBI patients. In MNI space, Fig. 4 shows the abnormal MEG slow-wave generations from two separate MEG exams in these patients. Very good test-retest-reliability was obtained, with the intra-class correlation coefficient (ICC) values of 75%, 81%, and 83% using the Zcmax, spatial correlation of spatial Z-score maps, and coordinates of the centers-of-mass, respectively (see D.3.7 for details). These preliminary results support Hypothesis 1. **Figure 4 - See attached document.**

C.5 IASIS Potentiates Endogenous Slowwaves Immediately after a Treatment Session

Fig. 5 shows preliminary data from a HC subject who participated in one session of IASIS. Three MEG exams were performed: the first right-before IASIS, the second immediately after IASIS (i.e., within a few minutes), and the third 96 hours after IASIS, all during wakefulness. The left panel of Fig. 5 shows a typical train of IASIS pulses at 3.6 Hz repetition rate (see Section D.4.1). The right panel shows that no abnormal MEG slow-waves (delta-wave band) were detected in either the MEG exam before IASIS and 96 hours after, which would be expected for a HC subject. However, immediately after IASIS, above threshold MEG slow-waves were detected from mid-line precuneous, mid-line vmPFC, bilateral medial temporal near hippocampus and amygdala, left insular, and cerebellum. These areas closely match the known brain networks observed during delta-wave sleep [83,84]. Due to strong artifacts from the IASIS device (left panel), we cannot obtain meaningful MEG slow-wave images during the IASIS session. However, we believe that the potentiation of slow-waves started during the IASIS session.

These preliminary data suggest that immediately after an IASIS treatment session, MEG slow-waves are potentiated in the same brain networks of delta-wave sleep, which supports Aim 1 and Hypothesis 2. **Figure 5 - See attached document.**

C.6 Ultimate Reduction of PCS and Abnormal MEG Slow-waves Post IASIS Treatment Course in mTBI

We performed a pilot study to assess the ultimate changes in MEG slow-waves and PCS in 6 individuals with chronic mTBI who went through the IASIS treatment course. IASIS treatments were applied twice weekly for 6 weeks, with MEG exams and PCS assessments at baseline and follow-up. None of the individuals from this pilot study had adverse events or noted side-effects.

C.6.1. Ultimate pre- and post-IASIS changes in PCS and PCL scores: We found significant reductions of PCS in all 6 mTBI individuals. RPQ total scores across 16 categories were significantly reduced after the IASIS treatment (Fig. 6A) (paired group t-test, $t=5.80$, $p<0.01$, Cohen's $d=2.37$). Significant reduction was also found in the Sleep Disturbance sub-category of the RPQ (paired group t-test, $t=3.00$, $p<0.05$, Cohen's $d=1.22$). These preliminary results provide strong support for Aim 2 and Hypothesis 4. We also collected PCL scores in 4 out of the 6 participants. Compared with pre-IASIS PCL, there was a trend of reduction in Post- IASIS PCL score (paired group t-test, $t=1.90$, $p=0.15$, Cohen's $d=0.95$), which also supports Hypothesis 5.

C.6.2. Ultimate pre- and post-IASIS changes in total abnormal MEG slow-wave generation: Fig. 6B shows a striking reduction in total abnormal Z-scores (see D.4.3) that measured abnormal MEG slow-wave generation between the pre- and post-IASIS MEG exams. The change in total abnormal MEG Z-scores was significant (paired group t-test, $t=4.28$, $p<0.01$, Cohen's $d=1.75$). This preliminary result shows that IASIS ultimately reduced abnormal MEG slow-waves in these individuals. This finding supports Aim 1 and Hypothesis 3. Next, we correlated the change (i.e., (pre - post) / pre) in MEG slow-waves due to treatment with relative change in the total RPQ scores. Relative total abnormal MEG Z-score change significantly correlated with relative total RPQ score change ($r=0.84$, $p<0.05$, Fig. 6C). This finding supports Aim 3 and Hypothesis 6.

C.6.3. Ultimate pre- and Post-IASIS changes in PCS and MEG slow-wave imaging for individual participants: Here, detailed information is provided for individual participants. Fig. 7 shows the loci of abnormal MEG slow-waves pre- and post-IASIS treatment in each of the 6 mTBI participants.

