
injury or if it is a signature of ongoing neuronal rearrangement and healing that occurs at the site of the injury.

Specific Aim 1: To detect the loci of injury in Veterans with mTBI and assess the mechanisms underlying functional neuroimaging changes related to IASIS treatment, and for a subset of Veterans with remaining symptoms, additional Nexalin treatment, using rs-MEG slow-wave source imaging. Our voxel-wise rs-MEG source-imaging technique will be used to identify abnormal slow-wave generation (delta band) in the baseline and post-treatment MEG exams to assess treatment-related changes on a single-subject basis. Healthy control (HC) Veterans, matched for combat exposure, will be used to establish an MEG normative database. Test-retest reliability of MEG slow-wave source imaging for mTBI will also be examined.

Hypothesis 1: Veterans with mTBI will generate abnormal MEG slow-waves during the baseline MEG exam. Voxel-wise MEG slow-wave source imaging will show significantly higher sensitivity than conventional MRI in identifying the loci of injury on a single-subject basis. The test-retest reliability of MEG slow-wave source imaging is expected to be high, with intra-class correlation coefficient (ICC) ≥ 0.75 between two sequential MEG exams.

Hypothesis 2: In wakefulness, slow-wave generation is a signature of ongoing neural rearrangement/healing, rather than a negative consequence of neuronal injury. IASIS treatment will enhance neural rearrangement/healing by initially potentiating slow-wave generation immediately after each treatment session.

Hypothesis 3: IASIS will ultimately reduce abnormal MEG slow-wave generation in mTBI by the end of the treatment course, owing to the accomplishment of neural rearrangement / healing. In Veterans with mTBI who finish IASIS treatment, but not in the sham group, MEG source imaging will show a significant decrease in abnormal slow-waves at post-treatment exam. Such significant decreases will also be evident in both the voxel-wise and overall abnormal MEG slow-wave measures.

Specific Aim 2: To examine treatment-related changes in PCS and PTSD symptoms in Veterans with mTBI. PCS and PTSD symptoms will be assessed at the baseline and post-treatment follow-up visits.

Hypothesis 4: Compared with the sham group, mTBI Veterans in the IASIS treatment group will show significantly greater decreases in PCS symptoms between baseline and post-treatment assessments.

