D.4.3. IASIS's immediate effect of slow-wave potentiation -- pre- and post-session rs-MEG changes: To achieve this goal, we will perform three pairs of pre- and post-session rs-MEG exams at the beginning, midpoint, and the end of the IASIS treatment course: in Visit 3 for the 1st IASIS session (S1), Visit 9 for the 7th IASIS session (S7), and Visit 14 for the 12th IASIS session (S12). The post-treatment rs-MEG will be performed within 30 minutes immediately after the treatment session. Two-factor mixed-design repeated measures ANOVA with covariates, equivalent to linear mixed effect model, will be applied for statistical analysis. We will: 1) assess the within-subject significance of the immediate slow-wave potentiation due to IASIS session by comparing the voxel-wise Z-score and total abnormal MEG Z-scores between pre- and postsession exams; and 2) assess the between-group treatment effect by comparing IASIS with Sham. The total abnormal MEG Z-score is calculated by summing up the Z-score from all voxels that showed statistically significant slow-wave generation. The dependent variables at both time points are either voxel-wise Z-scores or total abnormal MEG Z-scores, and the predictors are time (pre- and post-session), group (IASIS versus Sham), and their interaction. Veterans receiving IASIS treatment but not sham are expected to show significantly increase rs-MEG slow-wave generation in post-session rs-MEG exam immediately after the treatment session (Hypothesis 2). The preliminary result in C.5 (Fig. 5) supports this hypothesis.

D.4.4. Ultimate slow-wave reduction following the IASIS treatment course -- pre- and post-treatment rs-MEG exams: Participants in mTBI-IASIS group will participate in the 6-week IASIS treatment, whereas those in mTBI-Sham group will participate in a sham treatment for the same time period. To assess the ultimate effect of the IASIS treatment course, the 1-week post-

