treatment follow-up rs-MEG in Visit 15 will be compared with the baseline rs-MEG in Visit 2 (Fig. 10). The focus of our analyses are the pre- and post-IASIS change in the abnormal MEG slow-wave generation for both voxel-wise Z-score maps and the total abnormal MEG Z-scores. Two-factor mixed-design repeated measures ANOVA with covariates will be used to: 1) assess the within-subject treatment effect by comparing the voxel-wise Z-score and total abnormal MEG Z-scores between pre- and post-treatment exams; and 2) to assess the between-group treatment effect by comparing IASIS with Sham. Participants receiving IASIS treatment, but not sham, are expected to show significantly reduction in abnormal rs-MEG slow-wave generation in post- over pre-IASIS exams (Hypothesis 3). Preliminary result in C.6.2 and C.6.3 (Figs. 6B and 7) supports this hypothesis.

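### The MEG hypotheses predict a significant change in IASIS but not in sham, and no section says whether that pattern or the group-by-time term decides them

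*Combined protocol and SAP*

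**What the plan says.** **Hypothesis 3.** Section 6 states "In Veterans with mTBI who finish IASIS treatment, but not in the sham group, MEG source imaging will show a significant decrease". D.4.4 repeats the form: "Participants receiving IASIS treatment, but not sham, are expected to show significantly reduction in abnormal rs-MEG slow-wave generation". The power analysis in D.8 restates Hypothesis 3 with the same contrast between a decrease in IASIS and none in sham.

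**Hypothesis 2.** Section 6 says only that "IASIS treatment will enhance neural rearrangement/healing by initially potentiating slow-wave generation immediately after each treatment session". It has no sham clause and does not mention significance. The sham clause appears in D.4.3: "Veterans receiving IASIS treatment but not sham are expected to show significantly increase rs-MEG slow-wave generation in post-session rs-MEG exam".

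**Analysis.** Both sections plan a two-factor mixed-design repeated-measures ANOVA with covariates. In D.4.4 the first listed purpose is to "assess the within-subject treatment effect by comparing the voxel-wise Z-score and total abnormal MEG Z-scores between pre- and post-treatment exams" and the second is "to assess the between-group treatment effect by comparing IASIS with Sham". D.4.3 has the same pair for pre- and post-session exams. D.4.3 lists time, group and their interaction as predictors; D.4.4 does not list its terms. Neither section gives one test precedence.

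**Comparison.** Hypothesis 4 is worded as a between-arm contrast: "Compared with the sham group, mTBI Veterans in the IASIS treatment group will show significantly greater decreases in PCS symptoms". Hypothesis 5 follows it for PTSD symptoms.

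**The concern.** A significant result in one arm and a non-significant result in the other do not show that the arms differ. The two labels are separate tests against zero, and neither measures the IASIS-minus-sham difference. With two possible criteria and no stated choice between them, the same data could support or refuse the MEG hypotheses depending on which is applied.

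Both directions of error matter:

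- A change common to both arms (regression to the mean, habituation to the scanner, a placebo response) can by chance reach significance in IASIS and miss it in sham.
- If sham also changes enough to be significant, the wording fails even when IASIS changes clearly more.

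MEG change is the stated primary goal, and B.4 promises evidence that does not depend on placebo effects. Only the between-arm contrast can deliver that.

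**Working it through.** **1. The plan's own figure.** D.8 gives, for Hypotheses 2 and 3, Cohen's f > 0.45, two-tailed alpha 0.01, 50 per arm and power > 0.98. It does not name the term tested. Assume a pre-post correlation of 0.5 (the documents give none), N = 100, m = 2 time points and an F test on 1 and 98 df.

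- Repeated measures, between factors: λ = f²·N·m / (1 + (m − 1)ρ) = 0.2025 × 200 / 1.5 = 27.0, power 0.994.
- Repeated-measures interaction: λ = f²·N·m / (1 − ρ) = 0.2025 × 200 / 0.5 = 81, power about 1.00.
- One-way ANOVA: λ = f²·N = 20.25, power 0.968.

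The first two satisfy the stated > 0.98. The between-factors option also lies closest to the plan's other two figures: 0.959 at f = 0.38 (stated > 0.95) and 0.855 at f = 0.32 (stated > 0.85). So the stated power is reproducible, but it does not show that the interaction is the deciding test.

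**2. Equal true change in both arms.** Inputs: n = 50 per arm and two-sided alpha 0.01, both from D.8. Further assumptions: normal change scores, independent arms, no covariates, no dropout. Let δ be the common mean change in SDs of the change score, and p the probability that one arm is significant in the predicted direction:

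p = P(T > 2.680), where T is noncentral t with 49 df and noncentrality δ√50.

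The arms are independent, so P(IASIS significant, sham not) = p(1 − p).

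| δ (SD) | p | p(1 − p) |
|---|---|---|
| 0 | 0.005 | 0.5% |
| 0.1 | 0.029 | 2.8% |
| 0.2 | 0.113 | 10.0% |
| 0.3 | 0.299 | 21.0% |
| 0.38 | 0.50 | 25.0% (maximum) |
| 0.5 | 0.799 | 16.0% |
| 0.6 | 0.936 | 6.0% |
| 0.8 | 0.998 | 0.2% |

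Simulation of 100,000 trials at δ = 0.379 gave 24.9% for the pattern. The group-by-time test on the same data rejected in 0.99% of trials, 0.48% in favour of IASIS. That rate does not depend on δ. At alpha 0.05 the maximum is again 25.0%, at about 0.28 SD, against 2.4% in favour of IASIS for the interaction.

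**3. A real IASIS advantage with some sham change.** These scenarios are illustrative and not taken from the documents. The true difference in change is 0.7 SD, its standard error is √(2/50) = 0.2, so the noncentrality is 3.5. With 98 df and critical value 2.627, the interaction has power 80.6%.

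- IASIS 1.1 SD, sham 0.4 SD: IASIS is significant almost always, and sham is non-significant with probability 1 − 0.562. The pattern is met in 43.8%.
- IASIS 1.2 SD, sham 0.5 SD: the pattern is met in 1 − 0.799 = 20.1%.

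The true advantage is the same in both cases, but the chance of meeting the pattern halves because sham changed slightly more.

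**The case against.** The strongest reply is that the sham clauses are predictions and not decision rules. D.4.3 and D.4.4 say what participants are expected to show. The planned model has two factors, D.4.3 includes the interaction, both sections list a comparison with sham, and Section 6 frames the MEG aim as change relative to sham. If the between-group test must also be significant, the false-positive rate in favour of IASIS cannot exceed about 0.5%. This stands in part: the right test is already planned. What is missing is any statement that it decides, and Hypothesis 3 carries the other criterion in all three places where it is stated.

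It is also fair that D.5 lists the same two tests for Hypothesis 4 without ranking them. The list alone therefore does not set the MEG hypotheses apart. Their wording does, because Hypotheses 4 and 5 point to the between-arm contrast.

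Three stronger readings are tempting, and the documents do not support them:

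- *That a quarter of such trials would give a false IASIS effect.* The 25% is the mathematical maximum of p(1 − p), reached near one value of the shared change. The pilot in C.6 had six participants and no sham arm, so nothing fixes that value here.
- *That the plan would reject a clear IASIS advantage because sham was significant.* No section says so. It follows only if the wording is applied literally.
- *That Section 6 words Hypothesis 2 as significant in IASIS but not in sham.* It does not. That form is found only in D.4.3.

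The calculation also covers one outcome at one comparison. Requiring both the voxel-wise and the overall measure, as Hypothesis 3 may imply, would lower the rate. Accepting any one of the three session pairs for Hypothesis 2 could raise it above 25%.

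**Conclusion.** The concern holds as a defect in the decision rule and does not show that the planned model is wrong. Hypothesis 3 in Section 6, D.4.4 and D.8, and Hypothesis 2 in D.4.3, are framed as a contrast of significance labels. Hypothesis 2 in Section 6 lacks a comparator. No section names the deciding test.

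If the label pattern is used as the criterion, the false-attribution rate at alpha 0.01 with 50 per arm is 0.5% with no shared change, rises to a 25% ceiling near 0.38 SD and falls off for larger shared changes. The group-by-time test holds it at about 0.5%. These figures assume normal change scores, independent arms, complete data and a single outcome. The ceiling does not depend on the sample size; only the shared change at which it occurs does. Where this trial would fall in the range cannot be known from the documents.

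**What to change.** - In D.4.3 and D.4.4, state that Hypotheses 2 and 3 are each decided by the group-by-time interaction, reported as the IASIS-minus-sham difference in change with a confidence interval. List the model terms in D.4.4 as D.4.3 does.
- Apply this to the MEG measures the plan already names: the total abnormal Z-score, and the voxel-wise scores with their planned correction. Making the total score the sole endpoint would be a separate decision and is not part of this change.
- Reword Hypothesis 3 in Section 6, D.4.4 and D.8 as a significantly greater decrease than sham. Reword Hypothesis 2 in Section 6 and D.4.3 as a significantly greater post-session increase than sham. Both then match Hypotheses 4 and 5.
- Report within-arm changes descriptively, and drop the expectation that sham be non-significant as a condition for support.

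**Cost.** No new data are needed, and the interaction is already explicit in the D.4.3 model. Within-arm p-values lose their confirmatory role. Section 20 records that visits stopped on 09/30/2022, so the amendment should be dated and should say whether it was made before or after unblinding. How Hypothesis 2 combines its three session pairs (Visits 3, 9 and 14) remains open and is not settled by this change.
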